#### 4. Risks & Anticipated Benefit Analysis

- a. Risks associated with participation in this study will include low to moderate cardiovascular and/or muscular fatigue, also known as delayed onset muscular soreness (DOMS), associated with a new mode of activity/bodily movements that may or may not be a part of the participant's normal routine. Aerobic and resistance training will result in an increase in heart rate which may be uncomfortable for participants. Additionally, resistance training may cause an increase in heart rate and blood pressure as a result of low to moderate exertion. Cardiovascular and/or muscular fatigue and DOMS are normal for adults to experience at the start of physical activity. It is also normal for DOMS to occur with adults who have a history of being physically active. Risks associated with a vertical jump include knee discomfort. To minimize knee discomfort, the participant will complete the assessment on an exercise mat which will soften the impact when landing. The participant is also permitted to complete one jump or no jumps at all, if applicable.

BIA is free of radiation and there are no known associated risks with this. The participant, however, may experience emotional discomfort from his/her body weight, body fat, and/or waist being measured. The PI will provide encouragement to the participant and remind them of the purpose of the research study. The PI will also ask the participant if he/she would rather not know their individual measurements. Lastly, the participant will be reminded that he/she may withdrawal from the research study at any time.

- b. To minimize cardiovascular and muscular fatigue (DOMS) associated with a new mode of activity/bodily movements, participants can withdraw from the activity and/or exercise session at any time. Also, weeks one and two of the study will only use the participant's body weight to allow for a gradual adaptation of new activity/bodily movements. Participants will also be introduced to the new movement before it is introduced as a part of the program. To minimize discomfort associated with an increase in heart rate, participants will be reminded that they can take rest as needed and that they may also withdraw from the session and/or study whenever they choose. To minimize the effect that resistance training can have on blood pressure, the National Strength and Conditioning Association (NSCA) recommends aerobic, steady-state activity, such as walking proceed resistance training sessions. A 10-minute recovery period is a part of the 60-minute training session. During this time participants will walk or ride a non-weight bearing cardio machine.

Apparently healthy participants and/or those participants cleared by a physician to participate, still may be terminated by the principal investigator if participants' ratings of perceived exertion with an activity is too high. The Borg Rating of Perceived Exertion Scale is a scale used to monitor intensity during exercise. This scale has since been updated to the revised category ratio scale, CR10. The scale originally went from 6 to 20 with 6 being no exertion at all and 20 being maximal exertion. The revised/updated scale goes from 0 to 10. The scales correlate with exercise heart rates. Three revised CR10

color-coded posters will be hung around the dance studio. Participants will be asked to rate themselves throughout each 60-minute session. A detailed description of the scales is included with the IRB materials that are attached.

- c. The participants will be the direct beneficiaries of this study. Currently, there are limited to no opportunities for community residents to be physically active. Somerset County has the highest physical inactivity and physical health levels among surrounding counties. Expected benefits include improved weight maintenance, body composition, and health-related physical fitness. Participants can also expect to learn proper form and technique with flexibility, calisthenics, and resistance training exercises. Participants will also gain an understanding of how they can maintain physical activity levels despite the conclusion of the intervention. This study will contribute to existing research on health-focused community-health intervention programs in rural areas.
- d. Since the study is open to Somerset County community residents, the benefits will be distributed fairly. Participants will engage in the same program and receive the same services. It must be noted that participants may receive different levels of benefits based on individual motivation, consistency, and initial starting point in regards to physical activity. Children are not included in this study because children require a different training regime due to physical and neurological limitations associated with participation in a training session. Additionally, it is not appropriate for pregnant women to participate in this program. It would be difficult to assess changes in body composition and components of physical fitness as pregnant women undergo physiological changes that are relevant to being pregnant. For example, pregnant women may have a higher resting heart rate, lower aerobic capacity and/or exercise tolerance, and higher body fat levels. The purpose of this program contradicts some of the changes expected to take place with pregnant women and therefore the risks associated with their participation outweigh the potential benefits.

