- d. Somerset County Health Department will assist in advertising for the project. Subjects are not being selected based on any specific characteristic(s). Any interested adult in Somerset County can participate. The project is limited to 15 individuals and therefore participation is on a first come-first serve basis.
- e. The project will be advertised through Somerset County Health Department and the surrounding businesses and organizations. All interested adults that reside in Somerset County are welcome to participate if space is still available.

3. Procedures

- a. Participants will be asked to participate in a health screening and preliminary fitness tests after the informed consent has been signed and returned. Participants will be asked to respond with a yes or no to the following questions as a preparticipation and/or health screening tool.
  1. Do you participate in regular exercise?
  2. Has a physician or other qualified health care provider ever diagnosed you with cardiac, peripheral vascular, cerebrovascular disease, or Type 1 or 2 diabetes?

3. Do you have any signs or symptoms suggestive of cardiovascular, renal, or metabolic disease including but not limited to: pain/discomfort in the chest, neck, jaw, or arms; shortness of breath at rest or with mild exertion; dizziness during exercise, ankle edema, palpitations (awareness of rapid beating of the heart) or tachycardia; or unusual fatigue or shortness of breath with usual activities?

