The American College of Sports Medicine (ACSM) screening on a separate attachment will show how medical clearance is determined. Since the ACSM screening is limited in some regard, a Physical Activity Readiness Questionnaire Plus (PARQ+) will also be used as a precautionary measure prior to participation to gather additional information. The PARQ+ is located on a separate attachment. There is a line drawn through specific information related to a condition and/or medication because that information is not needed. The PARQ+ will be printed for the participants and the “please list” will be blacked out so that participants do not include this information. The information collected from the PARQ+ is only used to confirm whether or not the participant will need to obtain medical clearance prior to participation in any of the assessments and activities. The information is also used to determine proper exercise prescription for the intervention based on the participant’s current state of health. The participant will be asked to sign the PARQ+ and return it to the PI. The information collected from this will be stored in a sealed envelope that will be kept in a locked cabinet in the PI’s office. The PI is the only individual who has a key to the cabinet.

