An ACSM screening algorithm and the PARQ+ will be used to determine if a participant needs medical clearance prior to participation in the preliminary fitness tests which is completed a week before the program begins. The preliminary fitness tests will include the curl up, the pushup, bench press, vertical jump, and the Rockport 1-mile or 1.5 mile walk test. The purpose of the fitness test is to acquire baseline data about physical fitness levels before implementation of the intervention. The preliminary fitness test will not be used to determine if an individual can or cannot participate. Participants will complete a Bio-electrical Impedance Analysis (BIA), body weight, and waist circumference measurements before and after the study. The BIA will be used to determine percent body fat, skeletal muscle, and body mass index. The PI will program the BIA device. The participant will be asked to step on a scale and hold the handle of the BIA device. The participant will be asked to hold the BIA device for up to 5 seconds until the device completes the scan. The weight of the BIA device is approximately 12 ounces. BIA devices are available for the public and may be purchased by the public. To measure the participant’s waist circumference, a tape measure will be placed around the participant’s waist on the outside of their shirt. The participant will be asked to identify where their belly button is and the participant will wrap the tape measure around their waist. One inch below the participant’s belly button is where the participant will be asked to place the tape measure. The BIA and waist circumference measurements will be conducted in the exercise science lab located in the Department of Kinesiology in Hytche Athletic Complex on UMES campus.

These data collected from participants will be recorded and stored on a password protected university-owned laptop. The participant’s middle name will be used as an

identifier until post assessments are complete. Post assessments are completed at the end of the program and will include all of the preliminary assessments.

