- a. This research includes the collection of protected health information. The participant's anthropometrics (body weight and waist circumference) and body composition (BIA) will be recorded at the beginning and again at the conclusion of the 12 weeks. The PI, however, will not be contacting health care providers for any reason. Participants are allowed to receive a copy of personal measurements and/or assessments to give to their physician if it is requested prior to the conclusion of the study. Pseudonyms will be replaced with numbers therefore it will be impossible to determine a specific individual's results at the conclusion of the study. The health screening will be an interview with the potential subject. The interview includes three questions to determine if medical clearance is needed prior to participation as a precautionary measure. The answers to

these questions will not be shared with anyone. The questions for the ACSM preparticipation screening include:

1. Do you participate in regular exercise?
2. Has a physician or other qualified health care provider ever diagnosed you with cardiac, peripheral vascular, cerebrovascular disease, or Type 1 or 2 diabetes?
3. Do you have any signs or symptoms suggestive of cardiovascular, renal, or metabolic disease including but not limited to: pain/discomfort in the chest, neck, jaw, or arms; shortness of breath at rest or with mild exertion; dizziness during exercise, ankle edema, palpitations (awareness of rapid beating of the heart) or tachycardia; or unusual fatigue or shortness of breath with usual activities?

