Contraindications associated with the addition of this body composition device include claustrophobia. In addition to this, subjects may be self-conscious or uncomfortable with wearing tight-fitted, spandex shorts and a sports bra or camisole. Other risks include emotional discomfort as a result of seeing the analysis results related to their body composition. To minimize risk associated with claustrophobia, subjects will be allowed to complete a practice analysis of which they will be allowed to remain fully dressed. If during or after the practice analysis, the subject chooses not to complete the Bod Pod assessment, the subject is free to leave the room but may continue with the intervention without this assessment. If after the practice analysis the subject desires to run through the real analysis but then midway through decides they do not want to, the PI may click the 'abort' button to stop the analysis to allow the subject to come out of the chamber. On the inside of the chamber, the subject also has the ability to stop the test as well. The subject would be informed that they may press the 'blue' button which is on the chamber seat. The chamber is not locked however the PI must open the door. To minimize the discomfort with the required attire, a large sheet will be placed over the room's front window. In addition, the subject may choose not to complete the Bod Pod analysis at all. The accuracy of the analysis requires tight-fitted clothing such as spandex and

this will be explained during the (updated) informed consent process. Lastly, to minimize emotional discomfort associated with seeing the results from the analysis, the subject will receive positive reinforcement and encouragement as having made it to the 8-week and/or 12-week point. The PI will emphasize to the subject that they should view the results as a motivational tool only.

To increase the accuracy of the Bod Pod analysis, subjects should restrict their eating and exercise up to two hours before the assessment takes place. As a result, all the subjects will be tested on a non-intervention (exercise) session day of their choice. Subjects may be hungry since they would not have eaten for two hours and therefore, the PI will have a supply of snacks in the room for the subject after the assessment. Snacks will include the normal post-intervention snacks that the subjects are already familiar with. These snacks include dried fruit, nuts, and protein bars.

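### Section 4a declares BIA free of known risk without addressing its electrical nature, and no visible screening step links an implanted electronic device to the BIA scan

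*Combined protocol and SAP*

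**What the plan says.** **Risk statement.** Section 4a reads "BIA is free of radiation and there are no known associated risks with this". The only harm it then attaches to the body measurements is emotional discomfort. Section 4b, on minimising risk, does not mention BIA.

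**Procedure.** Section 3a schedules it for everyone: "Participants will complete a Bio-electrical Impedance Analysis (BIA), body weight, and waist circumference measurements before and after the study". It describes a device of about 12 ounces and states: "The participant will be asked to hold the BIA device for up to 5 seconds until the device completes the scan". No check before the scan is described. Section 8 says the grant buys a home BIA device; no model or manufacturer's instructions are given.

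**Entry.** Section 2 admits adults from 18 with no upper age limit, first come, up to 15 people. Section 4d rules out pregnant women. No exclusion for cardiac disease or implants is stated, and section 4b expects some participants to be physician-cleared.

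**Screening.** Section 9a says "The interview includes three questions to determine if medical clearance is needed prior to participation as a precautionary measure". The cardiac question is "Has a physician or other qualified health care provider ever diagnosed you with cardiac, peripheral vascular, cerebrovascular disease, or Type 1 or 2 diabetes"; the other two concern regular exercise and signs or symptoms. A second tool is used, but "The PARQ+ is located on a separate attachment". Of that form, sections 3a and 9a say "There is a line drawn through specific information related to a condition and/or medication because that information is not needed".

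**The other device.** The amendment on the Bod Pod says "Contraindications associated with the addition of this body composition device include claustrophobia". It lets a subject decline that test and stay in the intervention.

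**The concern.** A risk section should address the hazards that belong to the procedure. For a measurement that is electrical by name, absence of radiation leaves the obvious question open: does the device carry a warning for people with implanted electronic devices? The question is not remote here, since age is uncapped and a cardiac diagnosis leads to a clearance decision rather than exclusion.

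What is at stake is participant safety in a measurement planned for everyone, and the accuracy of an unqualified statement made to the IRB. If the device's instructions do carry such a warning, nothing in the visible text would bring it to bear on the scan.

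**Working it through.** The plan gives no figure to reproduce. The check is a reading of the text plus one count.

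**1. Does the supplied text mention implants?** The three interview questions are printed twice, in sections 3a and 9a. Of these, 0 of 3 mention an implanted device. Nothing else in the protocol or amendment mentions an implant or pacemaker. The content of the PARQ+, ACSM algorithm and consent form is unknown.

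**2. Would a PARQ+ answer reach the BIA step?** Sections 3a and 9a give PARQ+ answers two uses: deciding whether medical clearance is needed, and setting the exercise prescription. Neither is a decision about BIA. Condition and medication detail is struck out and the listing prompt is blacked out. Even if a printed PARQ+ question touches on implants, no stated step carries the answer to the scan.

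**3. Does medical clearance cover BIA?** Two statements in section 3a differ:
- The PARQ+ paragraph (repeated in 9a) places clearance ahead of every assessment and activity, which would include BIA.
- The next paragraph ties clearance to the preliminary fitness tests and lists them: curl-up, push-up, bench press, vertical jump and the walk test. BIA is not on that list; it is introduced separately.

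On either reading, nothing says that the clearing physician is told of an electrical measurement. Section 9a adds that the investigator will not contact health care providers.

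**4. How many scans?** At most 15 participants × 2 time points (before and after) = 30. The amendment speaks of the pre-assessment in the past tense, so when it was written the post-assessment scans, at most 15, were still ahead.

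**5. How likely is it that an implant holder enrols?** The documents give no prevalence. For an assumed prevalence p and 15 independent enrolees, the chance of at least one is 1 − (1 − p)^15:

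| Assumed p | Chance of at least one among 15 |
|---|---|
| 0.5% | 1 − 0.995^15 = 0.072 |
| 1% | 1 − 0.99^15 = 0.140 |
| 3% | 1 − 0.97^15 = 0.367 |

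These are chances of enrolling such a person under assumed prevalences. They are not the chance that screening misses the implant, nor the chance of any harm.

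**The case against.** The strongest reply is that the hazard is not in the documents. They name no device model, reproduce no warning and report no event; the name of the method shows that it is electrical, not that it endangers anyone. This stands. A reader might infer that the 4a sentence is false for people with implants, but the documents do not show that. They show only that the sentence is unqualified and does not address the point.

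Second, the unsupplied attachments may already deal with it. Section 3a adds the PARQ+ because the ACSM screening is limited, and the strike-out is described as covering condition and medication detail, not the questions themselves. A reader might infer that no question anywhere asks about implants; that cannot be said. What survives is that the visible uses of the answers stop short of BIA.

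Third, one of the two clearance statements does put clearance before all assessments. That is a real safeguard on that reading, but the other statement is narrower and the two need reconciling.

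Fourth, two tempting readings of the text fail. Section 4a joins absence of radiation and absence of known risk with a plain conjunction; it does not derive one from the other. Nor is BIA without any way out: 4a reminds participants that they may withdraw from the study, and section 7a lets them decline parts of the fitness test. Neither, however, is a BIA-specific opt-out like the one written for the Bod Pod.

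**Conclusion.** The point holds in a limited form. Section 4a makes an unqualified statement of no known risk that does not address the electrical nature of BIA. The printed screening questions and all other supplied text are silent on implanted electronic devices. No stated step links a screening answer to the BIA scan, and section 3a is inconsistent on whether clearance comes before it.

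The size is at most 30 scans in 15 people. The 7% to 37% range rests wholly on assumed prevalences and should not be read as a risk of harm. That implanted devices are the matter to ask about is itself an assumption, which the device's own instructions would confirm or remove. No harm is asserted. If the attached PARQ+ already asks the question and the device instructions carry no such warning, what remains is the wording of 4a and the clearance inconsistency. The change is worth making because it bears on safety and costs little.

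**What to change.** 1. Reconcile the BIA sentence in section 4a with the warnings in the instructions of the device actually used. Check that the consent form agrees.
2. Unless the attached PARQ+ already asks it, add one yes/no question on implanted electronic devices, put to each participant before any BIA scan, including the post-assessment. Handle the answer as the device's instructions state. Where they advise against scanning, record BIA as not done and keep the participant's other assessments.
3. Reconcile the two clearance statements in section 3a, and the repeat in 9a, so that clearance explicitly covers BIA.

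**Cost.** One question, one corrected sentence and a wording change. The amendment already plans an updated consent process, so consent text can be revised at the same time. The analytic downside is possibly a participant without BIA values. One person of 15 is 1/15 = 6.7% of the sample for percent body fat, skeletal muscle and body mass index. The Bod Pod cannot supply that person's change from baseline, because the amendment schedules it only at weeks 8 and 12. Body weight, waist circumference and the fitness tests are unaffected.

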## 5. Privacy/Confidentiality

- a. Confidentiality of subjects' identification and information collected will be maintained on a password-protected laptop loaned by the principal investigator by UMES. The laptop is kept in locked office. The principal investigator is the only individual who will have access to the computer. The middle name of the subject will be used for assessing before and after intervention changes. The participant's middle name will be used to generate a pseudonym. The key/code for the pseudonym will be kept on the same file that data is being stored on. The principal investigator is the only individual who will see individual test results. The participant may be given their own results after completion of the assessments for personal use. The principal investigator will not share individual test results with anyone other than with the participant. Before and after test results will be used for research purposes to determine effectiveness of the intervention however, the middle names of the participants will be removed from the data/file since it will no longer be needed. The key/code will be deleted.
- b. Information collected from the participants will not be shared with other participants. The principal investigator is the only individual who will have access to the information collected. If participants would like to know the information being collected from

him/herself, this information will be shared with the participant. Information collected from each participant will be done on an individual basis in the exercise science lab. The exercise science lab is located in the Department of Kinesiology in Hytche Athletic Complex on UMES campus. The PI will put the data into an excel spreadsheet. The PI will ask each participant if he/she would like a copy. Each individual session for the collection of measurements and assessments will be by appointment only. The information collected from the participants will be stored on a password protected laptop that only the principal investigator has access to. The participant's middle name will be used to identify their pseudonym until the conclusion of the intervention. Once the intervention ends, the participant's middle name and pseudonym will be deleted from the key/file and numbers will replace the names.

6. Informed Consent

- a. See attachment.
- b. Interested participants may call, email, or access the google form through the link provided by the principal investigator on the invitation to participate. Once the participant expresses interest by providing their contact information, an individual appointment will be scheduled to explain the study and the procedures. The informed consent, ACSM screening algorithm, PARQ+, and supplemental informed consents, if applicable, will be explained to the participant. The participant will be given time to ask questions. If the participant is still interested in participating, he/she will be asked to sign the documents. At these individual meetings, each participant will be provided a copy of the informed consent for him/her to keep.
- c. The readability report for the informed consent was over 12th grade with an age of 19 to 20 years old.

7. Research Plan for Collection, Storage, and Analysis of Data

- a. Data will be collected using a tape measure and a bioelectrical impedance analysis (BIA) device. Participants will be asked to complete a fitness test which includes a bench press, vertical jump, pushup, curl up, and either a 1-mile walk or 1.5 run/walk test. Data collected is what the participant completes through counting or by using a stopwatch. Participants can choose not to complete some or all of the fitness test. The PI is responsible for supervising all sessions. The PI is certified through both national certifying organizations, the National Strength and Conditioning Association and the American College of Sports Medicine, for exercise program design, implementation, and safety. The PI is required to maintain three certifications through pre-approved continuing education through the certifying organization as well as maintaining a current Cardiopulmonary Resuscitation (CPR) and Automated External Defibrillator (AED) certification. Additionally, there is a licensed athletic trainer working in Hytche Athletic Complex.
- b. Data will be stored in an excel spreadsheet on a password-protected laptop loaned to the principal investigator from the university. The PI is the only individual who has access to the laptop.

- c. Data will be analyzed for the mean and standard deviation of pre and post individual assessment data as a result of the intervention sessions. ANOVA with significance set at  $p<0.05$  will be used to determine the significance of the change in body weight, composition, waist circumference, and measures of fitness that may or may not have occurred. The mean and standard deviation of scores, pre and post, will be calculated and reported.
- d. The PI is the only individual who will have access to the data. Participants may request a copy of personal measurements/assessments prior to the conclusion of the study as pseudonyms may be replaced with numbers.
- e. The data will be kept for three years at the conclusion of the study.
- f. After the three-year period, the file will be deleted from the computer and the deleted folder will be emptied.

8. Conflict of Interest

- a. Potential conflict of interest includes receiving a grant from Somerset County Health Department (SCHD) for the development and implementation of a health intervention program for adults in Somerset County. This research effort and collection of data is not a condition of the funding received. This project may be carried out without intentions of a publication and/or presentation however, it has the potential to contribute to a body of knowledge on community health interventions and how they may be implemented. Additionally, results obtained from this project will be useful in applying for additional funding opportunities that will benefit the surrounding community. A narrative will be shared with SCHD at the completion of the project however, no raw data will be shared. The narrative will include results from the data analysis. The funding covers the equipment that will be needed, supplies for the participants, and salary. Equipment will include items such as the most accurate BIA home device, medicine/physio balls, exercise mats, stretching bands, and dumbbells. Supplies will include items such as hand towels, water, sanitizing wipes, and post-session snacks. Salary will be given to the PI for development and implementation of the intervention. This conflict will not affect the level of risk to the study participants and will be disclosed in the informed consent. Additionally, disclosure of this conflict of interest will be included in publications and/or presentations of the study results.

9. HIPPA Compliance

- a. This research includes the collection of protected health information. The participant's anthropometrics (body weight and waist circumference) and body composition (BIA) will be recorded at the beginning and again at the conclusion of the 12 weeks. The PI, however, will not be contacting health care providers for any reason. Participants are allowed to receive a copy of personal measurements and/or assessments to give to their physician if it is requested prior to the conclusion of the study. Pseudonyms will be replaced with numbers therefore it will be impossible to determine a specific individual's results at the conclusion of the study. The health screening will be an interview with the potential subject. The interview includes three questions to determine if medical clearance is needed prior to participation as a precautionary measure. The answers to

these questions will not be shared with anyone. The questions for the ACSM preparticipation screening include:

1. Do you participate in regular exercise?
2. Has a physician or other qualified health care provider ever diagnosed you with cardiac, peripheral vascular, cerebrovascular disease, or Type 1 or 2 diabetes?
3. Do you have any signs or symptoms suggestive of cardiovascular, renal, or metabolic disease including but not limited to: pain/discomfort in the chest, neck, jaw, or arms; shortness of breath at rest or with mild exertion; dizziness during exercise, ankle edema, palpitations (awareness of rapid beating of the heart) or tachycardia; or unusual fatigue or shortness of breath with usual activities?

The ACSM screening on a separate attachment will show how medical clearance is determined. Since the ACSM screening is limited in some regard, a Physical Activity Readiness Questionnaire Plus (PARQ+) will also be used as a precautionary measure prior to participation to gather additional information. The PARQ+ is located on a separate attachment. There is a line drawn through specific information related to a condition and/or medication because that information is not needed. The PARQ+ will be printed for the participants and the “please list” will be blacked out so that participants do not include this information. The information collected from the PARQ+ is only used to confirm whether or not the participant will need to obtain medical clearance prior to participation in any of the assessments and activities. The information is also used to determine proper exercise prescription for the intervention based on the participant’s current state of health. The participant will be asked to sign the document. The information collected from this will be stored in a sealed envelope that will be kept in a locked cabinet in the PI’s office. The PI is the only individual who has a key to the cabinet.

- b. The responses from the interview will be used to determine if medical clearance is necessary to participate in the study as a precautionary measure.

